### 3.0 Objectives

**Aim 1: Elucidate merits of transdiagnostic sampling.** Within the two intervention groups (Group 1: n = 24, Active iTBS and Active iTBS + APT; Group 2: n = 24, Placebo iTBS and Placebo iTBS + APT), we expect that (1i) neurologic diagnosis (stroke, TBI) will not moderate the effect of Active iTBS or Active iTBS + APT on Maximum Cognitive Gain as assessed by the Modified Digit Span (MDS) and the Streamlined AMPS (AMPS).

**Aim 2: Obtain pilot data to inform estimation of treatment and practice effects.** We will gather pilot data regarding the magnitude and duration of treatment effects as well as MDS and AMPS practice effects. As we anticipate (2i) greater immediate gains in IADL performance (AMPS) after Active iTBS + APT when compared to Active iTBS alone, we will compare Maximum Cognitive Gains (MCG) on MDS with MCG on AMPS between the Active iTBS and Active iTBS + APT groups to determine if MCGs differ in magnitude. We will also determine if

Active iTBS + APT trend lines indicate an additive treatment effect of APT on MDS and/or AMPS. We also anticipate (2ii) some persisting treatment effects and to explicate these effects we will examine effects for Active iTBS and Active iTBS + APT in the short-term (post-pre-treatment), long-term (2 weeks after a session) and cumulatively across treatment sessions. Since the AMPS uses a unique task during each testing interval and MDS uses 1 of 6 alternate test forms, we will determine (2iii) presence and magnitude of practice effects by testing whether prior exposure to MDS or AMPS results in MDS or AMPS gains for Placebo iTBS.

**Aim 3: Explicate study attrition by perceived suitability of aspects the study design and the relationship between this perceived suitability and fatigue as well as mood.** We will test the ideas that (3i) Attrition rates do not differ by stroke and TBI groups, (3ii) Veterans across stroke and TBI have similar perceptions regarding suitability of the number and type of tests as well as number of study-days, and (3iii) perceived suitability is related to Veteran-reported fatigue and mood.

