**Figure 1. Four Step Screening Process: Summary of Exclusion Criteria by Steps**

For this within-subject placebo-controlled partially-blinded treatment protocol (Fig 2), we will enroll 48 medically stable Veterans with stabilized recovery trajectories after a stroke or a TBI and who have a homogeneous level of moderately impaired cognitive function persisting after standard rehabilitation.

An equal number of Veterans with stroke/TBI (24-stroke; 24-TBI) will be enrolled, but we will over-sample females (Figure 2). For each iTBS group to include an equal number of Veterans with stroke/TBI, Veterans will be randomly assigned by diagnostic groups, to receive Active iTBS or Placebo iTBS. To measure immediate effects (ImE), an equal number of Veterans with stroke/TBI within each iTBS group will be randomly assigned to be tested with the Modified Digit Span (MDS) or AMPS, three times at 30 min intervals. Persisting effects (PE) tests will be administered to all participants at five timepoints including prior to and after Active iTBS or Placebo iTBS and 2-weeks later prior to the 2nd intervention, where all Veterans receive APT paired with their assigned iTBS (Active iTBS + APT or Placebo iTBS + APT). The alternate ImE test is then administered three times at 30 min intervals, followed by re-administration of all PE tests. Two weeks later, all PE tests are administered a 5th time (B4). ImE and PE measures are used to define magnitude and duration of cognitive change. Randomization (SAS Proc Plan) will be managed by one un-blinded researcher who will not provide interventions or conduct testing.

**Figure 2. Study Design (ImE = Immediate Effects Tests; AMPS = AMPS or MDS = Modified Digit Span; PE = Persisting Effects Tests for all participants; Study Day-1: Obtain Covariates and Treatment preparation information; B0 = Pre-Study-Day-2; B1 = Post-Study-Day-2; After 2-Weeks B2 = Pre-Study-Day-3; B3 = Post-Study-Day-3; After 2-Weeks B4 = Study-Day 4)**

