## 5.6 Data Analysis

**Sample Size to Estimate Effect Sizes.** Our total sample size of 48 participants is based on 80% power to detect an Effect Size (ES) of .90. For 80% power, sample size per group to detect a small ES (0.35) is 130, for a medium ES (0.60) it is 42 and to detect a large ES (0.90) it is 21 per group. To estimate a large ES of 0.90, 42 subjects are required to achieve 80% power. Thus, we plan for 48 participants and 12% attrition.

Published methods  will be used to examine the merits of transdiagnostic sampling (Aim 1i). Specifically, we will use MLM to determine if neurologic diagnosis (stroke, TBI) moderates the effects of the Active intervention (Group 1: n = 24, Active iTBS and Active iTBS + APT; Group 2: n = 24, Placebo iTBS and Placebo iTBS + APT) on Maximum Cognitive Gain (MCG) as measured with the MDS and the AMPS.

For Aim 2, we will inform estimates of effect sizes by testing the idea (2i) that MDS gains and AMPS gains differ for Active iTBS and Active iTBS + APT. As specified in Table 1, we will examine if gains differ in magnitude by computing the MCGs for each outcome (MDS and AMPS) by each intervention. For each outcome, we will compare the Average Active iTBS MCG with the Average Placebo iTBS MCG and the Average Active iTBS + APT MCG with the

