For Aim 3, we will compute study attrition as percent of participants dropping out after Study-Day 2 and after Study-Day 3. We will examine whether or not these attrition rates differ (3i) by stroke and TBI groups using chi-square. To examine if Veteran's with stroke and TBI have (3ii) different perceptions regarding the suitability of the number and type of tests and number of study-days, we will compare each group's average ratings, by suitability index, using t-tests. To explore the relationship between perceived suitability and fatigue as well as mood (3iii), we will compute Pearson correlations at each of the 5-timepoints (B0 through B4) between average ratings of suitability indices 1 through 3 and averages for each of the two fatigue measures and each of the five mood measures [5x (3x2) + 5x (3x5) = 105 correlations]. We will also compute correlations for average suitability indices 7 through 8 collected on Study-Day 4 (B4) with the averages from that same day for each of the two fatigue measures and each of the five mood measures [1x (2x2) + 1x (2x5) = 14 correlations]. We will test the significance of each correlation using Fisher Z test and results will be interpreted accordingly.

Aims 2 and 3 involve multiple comparisons. Bonferroni correction of type I error rate is very conservative, and, at this early research stage, it could mask important findings. Thus, we will control for false discovery rate (FDR) using an FDR level of .05.

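### The 80% power behind N = 48 fits a two-arm comparison; Aim 1's diagnosis-by-treatment interaction has about 30-33% power per outcome, so a non-significant result cannot confirm the predicted absence of moderation

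*Combined protocol and SAP*

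**What the plan says.** **Sample size (5.6).** The opening statement is "Our total sample size of 48 participants is based on 80% power to detect an Effect Size (ES) of .90". The numbers per group follow: 130 for an effect size of 0.35 and then "for a medium ES (0.60) it is 42 and to detect a large ES (0.90) it is 21 per group". The total is given as "To estimate a large ES of 0.90, 42 subjects are required to achieve 80% power", and the paragraph ends "Thus, we plan for 48 participants and 12% attrition". It names no test, alpha, sidedness, outcome or aim.

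**Aim 1 analysis (5.6).** "we will use MLM to determine if neurologic diagnosis (stroke, TBI) moderates the effects of the Active intervention", with Maximum Cognitive Gain (MCG) on the MDS and the AMPS as the outcome and 24 Veterans in each of the Active and Placebo groups.

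**Aim 1 expectation (3.0).** "neurologic diagnosis (stroke, TBI) will not moderate the effect of Active iTBS or Active iTBS + APT on Maximum Cognitive Gain". Neither section gives a margin, an interval or a rule for reading the result.

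**Allocation (5.1, text under Figure 1).** "An equal number of Veterans with stroke/TBI (24-stroke; 24-TBI) will be enrolled", randomised to Active or Placebo within diagnosis. Half of each diagnosis-by-arm group has the MDS as its immediate test at the first treatment session and half has the AMPS; they swap at the second session.

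**The concern.** A sample size is tied to one comparison. A reader of 5.6 sees a single power statement followed directly by the Aim 1 analysis, and may carry the 80% across. Moderation is a difference of two treatment effects, each estimated in half the sample, and it is estimated much less precisely than the overall arm effect.

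The direction of the prediction makes this matter more. In most trials low power works against the investigators' hypothesis. Here the expected finding is the null, so low power makes the expected finding likely whether or not it is true. Transdiagnostic sampling is the premise of the planned follow-on research. If stroke and TBI really respond differently, this analysis would usually fail to show it, and the plan gives no means of separating no moderation from too few Veterans.

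**Working it through.** **Inputs from the documents.** Effect size 0.90 and power 80%, with 21 per group, 42 in total and 48 at 12% attrition (5.6). 24 Active and 24 Placebo (3.0, 5.6). 24 stroke and 24 TBI, randomised within diagnosis (5.1), so 48/4 = 12 Veterans per cell.

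**Assumptions.** Two-sided alpha 0.05; the only 0.05 printed is for Aims 2 and 3 ("using an FDR level of .05"). SD = 1. The 0.90 is read as the difference between the stroke and TBI treatment effects, in SD units of MCG. One outcome is analysed at a time, with one MCG per Veteran per outcome.

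**Step 1: reproduce the plan's figures.** Two-sample t-test, two-sided 0.05, 80% power, noncentral t:

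| ES | Printed n per group | Required n per group |
|---|---|---|
| 0.35 | 130 | 130 |
| 0.60 | 42 | 45 (42 gives 77.6% power) |
| 0.90 | 21 | 21 (81.2% power) |

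The total is 2 x 21 = 42, and 42/0.88 = 47.7, rounded up to 48. One-sided tests would need 102, 36 and 16 per group and do not fit. The figure at 0.60 is slightly low but does not drive N. The sizing therefore matches a two-sided comparison of two groups. With all 24 per arm, power at 0.90 is 86%.

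**Step 2: standard errors at N = 48.**
- Arm effect: sqrt(2/24) = 0.289 SD.
- Interaction, (Active - Placebo in stroke) - (Active - Placebo in TBI): sqrt(4/m) with m per cell = sqrt(4/12) = 0.577 SD, twice as large.

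**Step 3: interaction power.** Noncentrality = 0.90/sqrt(4/m), with 4m - 4 degrees of freedom.

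| Case | m per cell | SE | Noncentrality | Power at 0.90 | Detectable at 80% | 95% CI half-width |
|---|---|---|---|---|---|---|
| All 48, sessions pooled | 12 | 0.577 | 1.56 | 33% | 1.65 SD | 1.16 SD |
| 42 completers | 10.5 | 0.617 | 1.46 | 30% | 1.77 SD | 1.25 SD |
| One outcome, one session | 6 | 0.816 | 1.10 | 18% | 2.40 SD | 1.70 SD |

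A simulation of 100,000 trials at 12 per cell also gave 33.2%. The half-width is the t quantile times the SE; for 48 Veterans, 2.015 x 0.577 = 1.16. At N = 48, power for interactions of 0.60 and 0.35 SD is 17% and 9%.

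**Step 4: more favourable readings, same 0.90.**
- One-sided test: 46% with 48 Veterans, 42% with 42.
- One interaction averaged over MDS and AMPS: 38-58% with 48, for a between-outcome correlation of 0.7 down to 0 (assumed range).
- Stroke versus TBI within the Active arm only, 12 versus 12: 56%.
- Covariates explaining 20-30% of the variance (assumed): 40-45%.

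None reaches 80%.

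**The case against.** **The plan never attaches the 80% to Aim 1.** This stands. The paragraph is headed as sizing for effect-size estimation, which is Aim 2's purpose, and Aim 2i uses Active-versus-Placebo t-tests that the formula fits. A reader might infer that the plan claims 80% power for moderation; the text does not say so. The gap is that it does not say which comparison the figure covers.

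**The 30-33% is not a ceiling.** This also stands. The plan does not specify one model per outcome, or the alpha and sidedness for Aim 1, and Step 4 shows readings with higher power. It would be wrong to call 33% the best case. Under every reading checked, power still falls short of 80%.

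**No rule says that non-significance will be declared as no moderation.** Correct. A reader might infer that rule from the predicted null, but the documents print no such rule, and the published method that 5.6 cites for Aim 1 is not reproduced there. What can be said is that no margin or interval is stated and that a non-significant test could not support the prediction.

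**Dropouts still contribute.** Section 5.7 keeps data collected before withdrawal. If all six losses came after the first treatment session, split evenly between the tests, about 45 Veterans would remain per outcome and power would be 31%, not 30%. The change is small.

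**It is a pilot.** This lowers the severity, and estimation is a proper aim for one. But Aim 1 is worded as an expected null, not as estimation.

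**Conclusion.** The concern holds in this form: the 80% power at an effect size of 0.90 describes a two-arm comparison, and the Aim 1 interaction does not have it. Per outcome, two-sided 0.05, power for a 0.90 SD interaction is about 33% with 48 Veterans, 30-31% after attrition and 18% within one session; the more favourable readings give about 38-58%. With sessions pooled, a true interaction of that size would be missed in roughly 67-70% of trials, and 80% power is reached only at about 1.65-1.8 SD. These figures rest on the assumed alpha and sidedness, and on reading 0.90 as the difference between the two diagnosis-specific effects.

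It would go too far to say that Aim 1 can yield nothing. It can give an estimate with an honest interval, but it cannot confirm absence of moderation. The point should be fixed, but it does not undermine the sample size for the two-arm comparison.

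**What to change.** Change the wording in 3.0 and 5.6; N, data collection and the mixed model stay as they are.

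1. In 5.6, state that 80% power at an effect size of 0.90 refers to a two-arm comparison, with its alpha and sidedness. Correct the figure printed for 0.60.
2. In 5.6, give the interaction power: about 30-33% per outcome for a 0.90 SD interaction under the stated assumptions, and 80% only at about 1.65-1.8 SD.
3. In 3.0 and 5.6, reword Aim 1 as estimation of the diagnosis-by-treatment interaction, reported with its 95% CI and with the Active-Placebo effect for stroke and TBI separately.
4. State that a non-significant interaction will not be taken as evidence that diagnosis does not moderate the effect. With an expected CI half-width of about 1.2 SD, Aim 1 is pilot information. An equivalence margin would add little here: even with an estimate of exactly zero, the interval would not be expected to fit inside a margin smaller than about 1.16 SD, which already exceeds the 0.90 that the plan calls large.

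The cost is a less favourable stated power and a weaker Aim 1 conclusion. No extra Veterans, visits or measurements are needed.

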
## List of Abbreviations

ABS: Agitated Behavioral Scale

AMPS: Assessment of Motor and Process Skills

APT: Attention Process Training

AUDIT-C: Alcohol Use Disorders Identification Test

BAI: Beck Anxiety Inventory

BRIEF-A: Behavior Rating Inventory of Executive Function

CDW: Corporate Data Warehouse

C-SSRS: Columbia Suicide Severity Rating Scale

CTI: Center for Translational Imaging

DAI: Diffuse Axonal Injury

DAST-10: Drug Abuse Screening Test

DLPFC: Dorsolateral Prefrontal Cortex

DKEFS: Delis-Kaplan Executive Function System

ES: Effect Size

FIM: Functional Independence Measure

fMRI: Functional Magnetic Resonance Imaging

FSS: Fatigue Severity Scale

GIMME: Group Iterative Multiple Model Estimation

IADLs: Instrumental Activities of Daily Living

ImE: Immediate Effects

iTBS: intermittent Theta Burst Stimulation

MCG: Maximum Cognitive Gains

MDS: Modified Digit Span Test

MLM: Mixed-Effects Linear Regression Model

MRI: Magnetic Resonance Imaging

NURIPS: Northwestern University Research Imaging Processing System

PCL: Posttraumatic Stress Disorder Checklist

PE: Persisting Effects

RBANS: Repeatable Battery for the Assessment of Neuropsychological Status

ROI: Region of Interest

TBI: Traumatic Brain Injury

WAIS-IV: Wechsler Adult Intelligence Scale Fourth Edition

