**Study-Day 2 (4 days after Study Day 1)(~8 hours):**

- 1. PE testing battery
- 2. A single session of **Active** iTBS or **Placebo** iTBS
- 3. Randomly assigned ImE test (MDS or AMPS), administered 3-times at 30 min intervals, each interval includes 5 to 15 min of rest).
- 4. PE testing battery
- 5. Suitability ratings 1-3

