Average Placebo iTBS + APT MCG using t-tests for continuous data and z-tests for binary data. Using MLM, we will also determine if Active iTBS is related to more MDS or more AMPS gains. The group (Active iTBS or Placebo iTBS) by time interaction parameter will be used to examine if Active iTBS has a differential trend compared to Placebo iTBS. For 2i, we will also use MLM to identify presence of an additive effect of APT by examining Active iTBS + APT trend lines. For both the AMPS and the MDS outcomes, the group (Active iTBS + APT or Placebo iTBS + APT) by time interaction parameter will be used to examine if the Active iTBS + APT has a differential trend compared to Placebo iTBS + APT. For each intervention we will also determine (2ii) presence of persisting effects of Active iTBS and Active iTBS + APT in the short-term, long-term and cumulatively. Using the PE measures specified in Table 1 and t-tests, we will compare each PE measure for Active iTBS with Placebo iTBS and for Active iTBS + APT with Placebo iTBS + APT. Significant results will be reported. For (2iii), we will use one-tailed t-tests to identify presence of practice effects for MDS and AMPS. We will compare MDS and AMPS average peak gains after Placebo iTBS with average peak gains after Active iTBS. If the average Placebo iTBS peak gain is greater than the average Active iTBS peak gain for either MDS or AMPS, then we will repeat analyses above (for 2i and 2ii) using ImE and PE measures after adjusting them for the detected practice effects.

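### The Maximum Cognitive Gain is undefined; read as best of three, it makes within-arm and practice gains positive from test noise alone, though not the Active-minus-Placebo contrast

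*Combined protocol and SAP*

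**What the plan says.** Aim 2 in section 3.0 promises: "We will gather pilot data regarding the magnitude and duration of treatment effects as well as MDS and AMPS practice effects". Part 2iii asks whether practice effects exist and how large they are, judged from gains in the Placebo iTBS arm. The same aim sets the MCG on the MDS against the MCG on the AMPS.

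The list of abbreviations only expands the name: "MCG: Maximum Cognitive Gains". Section 5.6 begins the magnitude analysis with "we will examine if gains differ in magnitude by computing the MCGs for each outcome (MDS and AMPS) by each intervention" and refers to Table 1 for the specification, but Table 1 (section 5.4) holds the inclusion and exclusion criteria. The rest has to be pieced together:

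- **Tests per session.** Study-Day 2 in section 5.1 lists "Randomly assigned ImE test (MDS or AMPS), administered 3-times at 30 min intervals". Study-Day 3 does the same with the other test.
- **Treatment comparison.** Section 5.6: "For each outcome, we will compare the Average Active iTBS MCG with the Average Placebo iTBS MCG", and likewise for the sessions with APT.
- **Practice check.** Section 5.6, with one-tailed t-tests: "We will compare MDS and AMPS average peak gains after Placebo iTBS with average peak gains after Active iTBS". If the Placebo figure is the larger, the immediate-effects (ImE) and persisting-effects (PE) measures are adjusted for practice and the 2i and 2ii analyses are rerun.
- **Other use of the scores.** Section 5.6 also plans group-by-time mixed models (MLM), which are not said to use the maximum.
- **Reference score.** The AMPS is in the PE battery given before treatment. The Study-Day lists show the MDS only after treatment; the pre-treatment battery has the WAIS-IV Digit Span instead.

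**The concern.** The highest of three noisy scores lies above a person's true level on average, even when nothing has changed. If the MCG is the best of three minus a single reference score, its arm average mixes real gain with this selection of favourable noise.

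Section 5.6 mentions no allowance for it. The pilot exists to hand a later trial a magnitude, a duration and a practice effect. A per-arm MCG quoted as a magnitude, or a Placebo peak gain quoted as practice, would overstate what it is meant to measure. Subtracting such a practice figure from PE measures, which are given once per timepoint, would over-correct them. Because the bias scales with each test's noise, it could also make one test look more responsive than the other.

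**Working it through.** **The plan's own figures.** The documents give no figure for the size or bias of the MCG. The nearest stated figure is the sample size: effect size 0.90, 80% power, 21 per group. A two-sample t-test at two-sided 5% (alpha assumed, as none is stated) gives 21 per group, so 42, and 42/0.88 = 47.7, rounded up to 48. That reproduces. It is a two-group effect, so the within-arm bias below should not be set against it.

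**Inputs.** Three ImE tests per session (section 5.1). Best of three is inferred from the wording. The within-person test-to-test SD (σ) and the reliability are not in the documents, so results are in units of σ, with a range.

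**Bias with no treatment and no practice effect.** Let x_j = true level + e_j, with normal e_j of SD σ, and MCG = max(x1, x2, x3) − x0.

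- Mean: 1.5/√π × σ = 0.846σ.
- SD: √(0.559 + 1) σ = 1.25σ, so the standardised bias is 0.846/1.25 = 0.68.
- Share of participants with a positive gain: 3/4, by symmetry.
- Mean of three minus x0, for comparison: mean 0, SD √(1 + 1/3) σ = 1.15σ.
- If the reference is test 1, the only listed option for the MDS: mean again 0.846σ, and the gain can never be negative.

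**Range.** If the three same-day errors correlate at ρ, the bias is 0.846 × √(1 − ρ) × σ. With independent errors and reliability r, it is 0.846 × √(1 − r) total SD.

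| ρ among same-day errors | 0 | 0.3 | 0.5 | 0.7 |
|---|---|---|---|---|
| Bias (σ) | 0.85 | 0.71 | 0.60 | 0.46 |

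| Assumed reliability r | 0.5 | 0.6 | 0.7 | 0.8 | 0.9 |
|---|---|---|---|---|---|
| Bias (total SD) | 0.60 | 0.54 | 0.46 | 0.38 | 0.27 |

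**Where it cancels.** Simulating Active minus Placebo on the same test with equal noise and no effect, at 12 and at 24 per arm, gives a mean difference of about 0 and two-sided type I error of 5.0%. A constant true shift of 1.0σ is recovered as 1.00σ. Fading effects of (1, 0.5, 0)σ and (1, 0, 0)σ give 0.60σ and 0.48σ, below the true peak and above the true means of 0.50σ and 0.33σ. The contrast is inflated only if Active scores are noisier: 0.846 × (k − 1)σ, which is 0.08σ, 0.21σ or 0.42σ for noise 10%, 25% or 50% larger.

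**Where it does not cancel.**

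1. *Placebo practice magnitude (Aim 2iii).* The expected Placebo peak gain is 0.85σ with no practice at all.
2. *Adjustment of PE measures.* The trigger compares arms, so the bias does not drive it. With no effect, the Placebo mean is the larger in about half of simulated trials, and significantly larger on a one-tailed test in about 5%. The size of the adjustment is not stated. If it is the Placebo peak gain, it carries the full bias into measures that are not maxima.
3. *Within-arm magnitudes by intervention.* Each carries the bias in the tables.
4. *MDS against AMPS.* The bias depends on each test's noise. The AMPS uses a different task every time and the MDS alternate forms are not validated (section 5.5), so equal noise cannot be presumed. With illustrative reliabilities of 0.9 and 0.6, the two biases are 0.27 and 0.54 SD, a difference of 0.54 − 0.27 = 0.27 SD from noise alone.

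**The case against.** The strongest reply is that the planned treatment comparisons are between arms on the same test, where the bias cancels. That stands. A reader might infer that the pilot's treatment effects are inflated; the documents do not support this. Under equal noise, and with the same number of completed tests, the contrast is unbiased under the null and understates a short-lived peak.

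A reader might also infer that practice will nearly always be declared present. A one-tailed test of Placebo gain against zero would indeed be positive in about 72% of trials with 12 participants and 95% with 24 when there is no practice. Section 5.6 does not specify that test. It compares "MDS and AMPS average peak gains after Placebo iTBS" with those after Active iTBS, and that statistic is not inflated. What stands is narrower: the aim seeks a magnitude from Placebo gains, and a peak gain is the wrong quantity for it.

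Nor do the documents show that the mean of three should replace the peak in the treatment contrast. In simulations with 12 against 12, an assumed ICC of 0.7 and baseline adjustment of both summaries, power was:

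| True benefit at tests 1/2/3 (SD) | Peak | Mean of three |
|---|---|---|
| 0.9/0.9/0.9 | 91% | 95% |
| 0.9/0.6/0.3 | 70% | 70% |
| 0.9/0.45/0 | 58% | 45% |
| 0.9/0/0 | 46% | 23% |

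For an effect of unknown duration the peak is a defensible choice.

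Finally, the formula is an inference and no pre-treatment MDS is listed, so a pre-to-peak MDS gain cannot be assumed. That limits how firmly any size can be stated, and the missing definition itself needs repair.

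**Conclusion.** The point holds in limited form. The MCG has no definition and its table pointer is wrong. On the natural best-of-three reading, a single arm's average MCG is biased upward by 0.85 within-person SD with independent errors, falling to about 0.46 if same-day errors correlate 0.7. With independent errors this is roughly 0.27 to 0.60 total SD for assumed reliability of 0.9 to 0.5. These sizes assume normal errors and values the documents do not supply.

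Affected are the Placebo practice magnitude, any peak-based adjustment of PE measures, the within-arm magnitudes, and the MDS-versus-AMPS comparison when noise differs. Not affected under equal noise are the Active-versus-Placebo t-tests and the Placebo-versus-Active practice comparison. The group-by-time models are not stated to use the maximum.

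**What to change.** In section 5.6:

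1. Give the MCG formula and its reference score for each test, and correct the Table 1 pointer.
2. Estimate practice as the Placebo mean change at fixed test numbers. As the MDS has no listed pre-treatment administration, use change from test 1 to tests 2 and 3, and note that the fixed form order mixes form difficulty with practice.
3. Do not adjust PE measures with a peak-based practice estimate.
4. Report per-arm and MDS-versus-AMPS magnitudes as fixed-time values from a mixed model of the three scores.
5. Report the MCG only as Active minus Placebo. It may stay as the summary in the treatment contrast.

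The cost is SAP wording; the scores are already to be collected. The downside is that stated within-arm gains will be smaller.
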